8.2 Potential Adverse Events (AEs)

Potential complications associated with the investigational device as with all other suture mediated closure devices may include, but are not limited to, the following:

- Allergic reaction or hypersensitivity to device components
- Anemia
- Arterial stenosis/occlusion
- Arteriovenous fistula
- Bleeding/hemorrhage
- Bruising
- Death
- Deep vein thrombosis
- Device entrapment
- Device failure/malfunction/misplacement
- Diminished pulses distal to closure site
- Embolism
- Extended Hospitalization / Delayed time to ambulation
- Hematoma
- Infection/sepsis

- Inflammation
- Intimal tear/dissection
- Ischemia distal to closure site
- Nerve injury
- Numbness
- Pain
- Perforation
- Pseudoaneurysm
- Retroperitoneal hematoma/bleeding
- Superficial vein thrombosis
- Surgical exposure/closure of common femoral artery
- Thrombus formation
- Vascular injury
- Vasovagal episode
- Vasoconstriction/vasospasm
- Wound dehiscence

8.3 Follow-up of Adverse Events

All adverse events observed from the time of enrollment throughout the duration of the study must be reported on the eCRF. All adverse events will be followed until resolution or stabilization of symptoms through study completion and/or the subject withdraws consent. Resolution means that the subject has returned to a baseline state of health. Stabilization means that the investigator does not expect any further improvement or worsening of the adverse event.

8.4 Causality Rating

The causal relationship of an adverse event to the investigational device will be rated as follows:

Not Related: An event for which an alternative explanation is conclusively identified - e.g., concomitant drug(s), concomitant disease(s), and/or the relationship in time suggests that a causal relationship is highly unlikely.

Possible: An event that is unlikely due to the use of the investigational device. An alternative explanation - e.g., concomitant drug(s), concomitant disease(s) - is inconclusive. The relationship in time is reasonable; therefore, the causal relationship cannot be excluded.

Probable: An event that might be due to the use of the investigational device. An alternative explanation is less likely - e.g., concomitant drug(s), concomitant disease(s). The relationship in time is suggestive.

Definitely: An event that is due to the use of the investigational device. The event cannot be reasonably explained by an alternative explanation - e.g., concomitant drug(s), concomitant disease(s).

8.5 Severity of Adverse Events

The severity of an AE will be rated as follows:

Mild	An adverse event that is easily tolerated by the subject, causes minimal discomfort and does not interfere with everyday activities.
Moderate	An adverse event that is sufficiently discomforting to interfere with normal everyday activities; intervention may be needed.
Severe	An adverse event that prevents normal everyday activities; treatment or other intervention usually needed.

8.6 Events Requiring Expedited Reporting

Expedited Events refer to events that the site principal investigator should report to the CRO/Sponsor within twenty-four (24) hours of knowledge of the event. The appropriate eCRF and related documents should be completed in the data management system.

If a non-serious AE becomes serious, this and other relevant follow-up information must also be reported using the appropriate eCRF.

The Sponsor will immediately conduct an evaluation of any unanticipated adverse device effects (UADEs). If the effect is determined by the Sponsor to present an unreasonable risk to the subject, all investigations or parts of the investigation presenting that risk will be

terminated as soon as possible. Termination will occur not later than five working days after the Sponsor makes this determination, and not later than 15 working days after first receiving notice of the effect.

The Sponsor will not resume an investigation terminated under these conditions without an additional IRB approval.

8.6.1 Expedited Events include:

1. Unanticipated Adverse Device Effects (as defined in section 8.1) will include events meeting either A or B as stated below:
 - A. Events meeting ALL of the following criteria:
 - Not included in the list of Anticipated Events (refer to section 8.2)
 - Possible, probable, or definitely related to the investigational device per the site principal investigator
 - Serious (meets any of the following criteria):
 1. Resulted in a life-threatening illness or injury
 2. Resulted in a permanent* impairment of a body structure or body function
 3. Required in-patient hospitalization or prolongation of existing hospitalization
 4. Resulted in medical or surgical intervention to prevent impairment to body structure or a body function
 - *(Permanent means irreversible impairment or damage to a body structure or function, excluding trivial impairment or damage)
 - B. Any other unanticipated serious problem associated with the investigational device that relates to the rights, safety, or welfare of subjects
2. Device Failures as defined in Section 13
3. Device Malfunctions as defined in Section 13
4. User Errors: A device is used by the investigator in a manner that is contrary to the IFU
5. All Deaths

8.7 Clinical Events Committee (CEC)

The CEC is composed of physicians who are interventional and/or non-interventional cardiologists, who are not participating in this study, and who do not have any investment with the study Sponsor. The CEC is charged with the review and classification of adverse events (AEs), including deaths. The CEC will establish rules outlining the minimum amount of data required and the algorithm followed in order to classify AEs. All members of the CEC will meet regularly to review and classify AEs. All appropriate data will be reviewed by the CEC. The CEC will forward a report of event reviews and classifications as outlined in the CEC charter.

8.8 Data and Safety Monitoring Board (DSMB)

The DSMB will be appointed to monitor the conduct of the study and subject safety by periodically reviewing data from the study. The DSMB will oversee the overall safety of current and future study subjects by protecting them from avoidable harm. The DSMB will review adverse events and other relevant study data and will recommend study termination if safety concerns warrant such action. The DSMB will also establish guideline criteria for recommending study termination, to the extent possible that the DSMB can predict adverse events or outcomes, before the proposed study begins.

The DSMB will be an independent committee with no direct involvement in the day-to-day undertaking of the study and no investment in the Sponsor. DSMB members and activities may overlap with the CEC as appropriate. The DSMB will consist of physicians, including one chairperson and a statistician who will provide an independent review of the data. The physicians will include an interventional cardiologist and vascular surgeon experienced in vascular closure to ensure appropriate review of vascular complications in the study. The DSMB report will detail all serious and unexpected adverse events or other unanticipated problems that involve potential risk to future study participants. If the DSMB has concerns regarding the study, the DSMB will notify the Sponsor, who will provide the relevant summaries to local IRBs. Actions taken by any IRB in response to safety concerns will be reported to the DSMB.

The DSMB will meet periodically throughout the study in order to assure close and timely monitoring of adverse events and outcomes. The operational details of the DSMB will be determined early in the study and formalized in the DSMB Charter.

The Sponsor and/or CRO will be responsible for working with the DSMB to ensure the DSMB Charter is developed. After the DSMB Charter has been finalized and approved by the DSMB, any changes or deviations to the plans in the charter will be documented in the minutes of the DSMB meetings.

Reports will be prepared by the Sponsor and/or CRO as requested by the DSMB Chairman and as required per the charter. In addition to safety data, the reports may include recruitment and retention rates, interim analyses and other information as requested by the DSMB Chairperson.

9 Risk Assessment

9.1 Risk Management Procedure

Subjects will be monitored closely throughout the study duration. Risks will be further mitigated through selection of qualified physicians, appropriate training, and study monitoring ensured by the following:

- Investigators who participate in the study will be experienced and skilled in endovascular techniques. Additionally, investigators, in conjunction with the investigational site, will have adequate resources for participation in a clinical study.
- The study has been designed to ensure treatment and follow-up of subjects are consistent with current medical practice.
- Each investigator will ensure oversight and approval of the study by their IRB prior to initiation of the clinical study at his/her investigational site.
- The investigator and study personnel will be trained on the clinical protocol and IFU for the investigational device.
- Subjects will be carefully evaluated against the eligibility criteria prior to entering the clinical study to ensure that their diagnosis and medical status are appropriate for participation.

- Subjects will be monitored throughout the follow-up period as defined in the study protocol. Subjects will have visits with the investigator or his/her designee to monitor the subjects' status pre-procedure, intra-procedure, and post-procedure.
- A DUS will be performed at 30 days post-procedure and repeated at 60 days if subject had an abnormal 30 day ultrasound to ensure adequate evaluation of the target limb access site.

9.2 Potential Benefits

Subjects enrolled in this clinical study will be monitored closely throughout the study and have regular assessments according to the investigator's standards of care. The data collected during the clinical study will provide further understanding how the Cross-Seal™ System is clinically beneficial. Potential benefits may include:

- Reduced Time-to-Ambulation (TTA)
- Reduced Time-to-Hemostasis (TTH)
- Improved quality of life

10 Centers for Medicare and Medicaid Services (CMS) Reimbursement

The Sponsor will seek applicable Medicare coverage in compliance with CMS requirements for this study. Based on the target study population including mean age, approximately 70% of subjects enrolled in this study will utilize CMS/Medicare reimbursement during their participation.

The study will be conducted in compliance with all applicable Federal regulations concerning the protection of human subjects found at 21 CFR parts 50, 56, and 812, and 45 CFR part 46. In addition, the study will be registered with the National Institutes of Health National Library of Medicine's ClinicalTrials.gov.

The Sponsor has a legal responsibility to the regulatory authorities to fully report all results of sponsored clinical studies. No investigational procedures other than those in this protocol shall be undertaken. The sponsor intends to submit a formal report to FDA following completion of the last subject visit required for primary endpoint analysis. Should the study be terminated early, the Sponsor will make every effort to expedite reporting of study

results to the FDA database for public review. Any use of the investigational device by an investigator that is contradictory to the application described in the IFU will be categorized as device misuse.

11 Monitoring

The Sponsor will perform monitoring functions within this clinical study and may be delegated to a CRO designate as needed. Study monitors will work in accordance with standard operating procedures (SOPs) and the approved Monitoring Plan. Any CRO monitors have the same rights and responsibilities as monitors from the Sponsor organization.

At the site, monitors will perform and verify the following:

- The adequacy and experience of the study center including Sponsor notification of any problems relating to facilities, technical equipment or medical staff
- Written Informed Consent has been obtained from all subjects prior to any study related procedures being performed and that data is recorded correctly and completely
- Source Document Verification (SDV): comparing data in the eCRFs to ensure they correspond with applicable source data, and to inform the Sponsor and investigator of any discrepancies, errors or omissions
- Ensure adherence to the protocol and applicable regulations at the investigational site and notify the Sponsor promptly of any deviations
- Evaluate subject compliance and support subject retention efforts at the site
- Device accountability and appropriate storage conditions are maintained according to the IFU

Data will be collected using eCRFs for this study. Investigative sites will enter data directly into the eCRFs via a web-based system. A Sponsor representative will provide training and technical assistance to the investigator and site staff on the procedural application, intended use, and performance characteristics of the investigational device. In addition, a Sponsor representative will schedule periodic, on-site visits to observe clinical procedures, under

supervision of the investigator, and to answer questions or concerns regarding the investigational device.

Given that on-site monitoring at some trial locations may be impacted due to the COVID-19 pandemic, the Sponsor has implemented both central and remote monitoring to maintain oversight of the clinical study and sites. This includes, but is not limited to, telephone and/or email contacts with the sites (to review study procedures, trial participant status, and study progress), remote review of de-identified source, remote access to electronic medical records (EMR), and frequent eCRF reviews. Given the ongoing and unpredictable nature of the COVID-19 pandemic, individual site variability on permitting remote EMR and/or the transmission of de-identified source, as well as continually changing local and state mandates governing travel, the Sponsor may have to adapt its monitoring processes regularly to fulfill its obligations as a Sponsor under federal law and regulations. The Sponsor will continuously assess each site and will monitor study data at the earliest possible opportunity, either in person or remotely.

12 Image Analysis

Duplex Ultrasound (DUS) of the femoral artery will be obtained at 30 days post-procedure (target limb only). In the instance of an abnormal DUS at 30 days, the subject will be required to conduct a repeat DUS at 60 days post-procedure.

All Duplex Ultrasound images obtained during the study will be anonymized and sent to a central core laboratory for independent analysis.

13 Device Failure and Malfunction

A device failure has occurred when the device is used in accordance with the IFU, but does not perform as described in the IFU, and also negatively impacts treatment of the study subject. Device Failures may include the following:

- Device used in study subject resulting in the occurrence of a major complication
- Unable to use RESET 1 Button
- Unable to deploy PLUNGER on device
- Unable to use RESET 2 Button

A device malfunction occurs when the device is used in accordance with the IFU and an unexpected change to the device contradictory to the IFU is observed, which may or may not affect device performance. Device Malfunctions may include the following:

- Device(s) with which insertion attempts were made, but was not used in the subject.
- Unable to observe bleeding back after sufficient dissection is performed
- Unable to deploy slider of Cross-Seal™ Device
- Needle dislodged after device deployment
- Unable to cut suture with Suture Trimmer
- Device is damaged in packaging
- Issues with use of Knot Tyer and/or Knot Pusher
- Suture break during device, Knot Tyer and/or Knot Pusher use
- Device packaging issue
- Device Sterility issue

Device malfunctions occurring in roll-in subjects will be additionally evaluated for potential relationship with the learning curve of the investigational device (e.g., operator applies excess tension to suture during pre-closure causing break)

In the case where a device has malfunctioned/failed, the investigator must make every possible effort to return the device to the Sponsor, unless there is a known contamination with an infectious disease (i.e. Hepatitis B, C or HIV).

14 Statistical Methods

14.1 Sample Size Determination

The sample size calculations were performed using PASS 2020 Version 20.0.2ⁱⁱⁱ. The appendix included the output from the software. The sample size for the study is based on power considerations for the primary effectiveness endpoint. As will be described below, this sample size should also provide adequate power for the primary safety endpoint.

14.1.1 Primary Efficacy Endpoint

The primary effectiveness hypothesis will be tested by comparing the primary effectiveness endpoint, mean time-to-hemostasis (TTH), against a performance goal (PG) of 15 minutes.

The comparison to the performance goal will be based on the following statistical hypothesis test:

$$H_0: \mu_{TTH} \geq 15$$

$$H_A: \mu_{TTH} < 15$$

where μ_{TTH} is the mean time-to-hemostasis in minutes.

The test will be based on whether the upper one-sided 97.5% confidence limit (based on a t-distribution)^{iv} is less than 15. Assuming similar performance to Perclose ProGlide®, with a mean time-to-hemostasis of 9.8 minutes and a standard deviation of 17 minutes the sample sizes for power levels from 80 to 90%

a Table 3: Primary Efficacy Endpoint Sample Sizes for Various levels of Power

Power	Sample Size	Maximum Observed Time (minutes) and still reject H_0
80.0%	86	10.8
81.4%	89	10.9
82.3%	91	10.9
83.1%	93	10.9
84.3%	96	11.0
85.0%	98	11.1

Successful rejection of the null hypothesis will mean that the PG has been met.

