14.2.10.1 Primary Efficacy Endpoint

The primary efficacy endpoint will be evaluated using the using the efficacy analysis set. The mean and standard error will be reported for the primary efficacy endpoint. A one-sample t-distribution will be used for calculating the upper 97.5% confidence limit.

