### 6.1 Primary Efficacy Endpoint

The primary effectiveness hypothesis will be tested by comparing the primary effectiveness endpoint, mean time-to-hemostasis (TTH), against a performance goal (PG) of 15 minutes.

The comparison to the performance goal will be based on the following statistical hypothesis test:

$$H_0: \mu_{TTH} \geq 15$$

$$H_A: \mu_{TTH} < 15$$

where  $\mu_{TTH}$  is the mean time-to-hemostasis in minutes.

The test will be based on whether the upper one-sided 97.5% confidence limit (based on a t-distribution) is less than 15. Assuming similar performance to Perclose ProGlide®, with a mean time-to-hemostasis of 9.8 minutes and a standard deviation of 17 minutes the sample sizes for power levels from 80 to 90%

Statistical Analysis Plan		Page 15 of 31
Sponsor Terumo Medical Corporation	Study Cross-Seal IDE Trial: Prospective, Multi-Center, Single Arm Study of the Cross-Seal Suture-Mediated Vascular Closure Device System	Version 1.4

a Table 1: Primary Efficacy Endpoint Sample Sizes for Various levels of Power

Power	Sample Size	Maximum Observed Time (minutes) and still reject $H_0$
80.0%	86	10.8
81.4%	89	10.9
82.3%	91	10.9
83.1%	93	10.9
84.3%	96	11.0
85.0%	98	11.1

Successful rejection of the null hypothesis will mean that the PG has been met.

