##### Summary Statements

Statistical Analysis Plan		Page 26 of 31
Sponsor Terumo Medical Corporation	Study Cross-Seal IDE Trial: Prospective, Multi-Center, Single Arm Study of the Cross-Seal Suture-Mediated Vascular Closure Device System	Version 1.4

A sample size of 86 achieves 80% power to detect non-inferiority using a one-sided one-sample t-test when the non-inferiority mean is 15.0 and the actual mean is 9.8. The data are drawn from a single population with an estimated standard deviation of 17.0. The significance level (alpha) of the test is 0.025.

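### At the planning SD of 17, the efficacy table's maximum passing mean is about 0.5 to 0.6 minutes too low in every row

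*Protocol*

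**What the plan says.** Protocol 14.1.1 tests "mean time-to-hemostasis (TTH), against a performance goal (PG) of 15 minutes". The decision rule there reads: "The test will be based on whether the upper one-sided 97.5% confidence limit (based on a t-distribution") is below 15. The planning assumption is performance like the reference closure device, "with a mean time-to-hemostasis of 9.8 minutes and a standard deviation of 17 minutes". Protocol 14.2.10.1 repeats the rule for the analysis itself: "A one-sample t-distribution will be used for calculating the upper 97.5% confidence limit". SAP 7.7.1 says the same. The software output in SAP 9.1 agrees, both on the level ("The significance level (alpha) of the test is 0.025") and on the design ("A sample size of 86 achieves 80% power to detect non-inferiority using a one-sided one-sample t-test").

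The table in Protocol 14.1.1 lists power, sample size and a third column, "Maximum Observed Time (minutes) and still reject H_0". For N = 86, 89, 91, 93, 96 and 98 that column reads 10.8, 10.9, 10.9, 10.9, 11.0 and 11.1 minutes. The same six values stand in the protocol synopsis and in SAP 6.1. Neither document says how they were obtained, and the efficacy output in SAP 9.1 contains no critical-mean column.

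**The concern.** The column is presented as the pass/fail threshold for the primary efficacy endpoint. If it came from the test and planning values stated just above it, a mean equal to the printed value would have an upper 97.5% limit just under 15. It does not, so a reader who uses the column would misjudge results near the boundary. For example, at N = 86 with an observed SD of 17, a mean of 11.0 meets the goal, although the table implies that it fails. The column also names no SD, so it can be read as a fixed cut-off, which a t-based rule does not have.

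**Working it through.** **Inputs.** Performance goal 15, planning mean 9.8, planning SD 17 and one-sided alpha 0.025, from Protocol 14.1.1 and the SAP 9.1 output. The sample sizes are those of the table.

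**Step 1: reproduce the plan's power column.** Power of the one-sided one-sample t-test is P(T < -t(0.975, n-1)), where T is noncentral t with n-1 degrees of freedom and noncentrality -(15 - 9.8)/(17/√n). This gives 0.80080, 0.81436, 0.82296, 0.83120, 0.84294 and 0.85037, identical to SAP 9.1. The inputs are therefore read correctly.

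**Step 2: compute the largest passing mean.** The rule is mean + t(0.975, n-1) × SD/√n < 15, so at SD 17 the boundary is 15 - t(0.975, n-1) × 17/√n. For N = 86: 17/√86 = 1.8332; t(0.975, 85) = 1.9883; product 3.6448; boundary 15 - 3.6448 = 11.3552.

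**Step 3: put the printed values back through the rule.** The upper limit at printed mean m is m + t(0.975, n-1) × 17/√n.

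| N | Printed maximum | Computed boundary | Gap (min) | Upper limit at printed value |
|---|---|---|---|---|
| 86 | 10.8 | 11.3552 | 0.56 | 14.445 |
| 89 | 10.9 | 11.4189 | 0.52 | 14.481 |
| 91 | 10.9 | 11.4596 | 0.56 | 14.440 |
| 93 | 10.9 | 11.4989 | 0.60 | 14.401 |
| 96 | 11.0 | 11.5555 | 0.56 | 14.445 |
| 98 | 11.1 | 11.5917 | 0.49 | 14.508 |

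One-decimal printing accounts for at most 0.05 minutes if rounded, or 0.1 if truncated. A normal quantile in place of t widens the gap (11.41 at N = 86).

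**Step 4: the worked example.** For a mean of 11.0 at N = 86 with SD 17, the upper limit is 11.0 + 3.6448 = 14.645, which meets the goal.

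**Step 5: check the parallel safety column.** One-sided 95% Clopper-Pearson lower limits for 72/78, 79/86 and 87/95 are 85.4%, 85.3% and 85.3%, all above 85.2%. One fewer success gives 83.8%, 83.8% and 84.1%, all failing. The safety thresholds in Protocol 14.1.2 are therefore correct, and the problem is confined to the efficacy column.

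**Step 6: what else could give the column.** The documents do not say. A 98.75% limit at SD 17 gives 10.82, 10.89, 10.94, 10.98, 11.05 and 11.09, which matches five rows after rounding but not N = 93. That test would have power of only 71.0% to 77.3%, not the 80% to 85% printed alongside. A 97.5% limit with an SD of about 19.7 fits all six rows, but no such SD appears in either document. Neither is put forward as the cause.

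**The case against.** The strongest reply is that nothing depends on the column. Success is decided by the confidence limit from the observed SD, no section uses the printed maximum as a criterion, and the sample size and power are right. That is true, and it limits the point to an erratum.

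A second reply is that the stated test fixes no maximum mean at all, because the cut-off moves with the observed SD. At N = 86 it would be 12.86 for an SD of 10 and 10.71 for an SD of 20 (illustrative values, not from the documents). In the second case the printed 10.8 would be slightly lenient. This is correct: the size of the error is conditional on SD 17. But 17 is the only SD the documents give, and it is stated in the sentence that introduces the table. The dependence on SD is also a reason against printing an unlabelled threshold.

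A third reply is that the column may follow the same rule with a different SD. So the check shows only that the column is inconsistent with the inputs of the power column (alpha 0.025 and SD 17); it does not show that a different test was used. That narrower statement is the one made here.

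Finally, because the printed values carry one decimal, the row-by-row gaps should be read as roughly 0.5 to 0.6 minutes.

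**Conclusion.** The concern holds. Given the stated 97.5% t-limit, the goal of 15 minutes and the planning SD of 17, all six printed maxima are too low, by 0.49 to 0.60 minutes, in each of the three tables. None is the largest mean that still rejects the null hypothesis. At SD 17 the error is conservative: the table makes the goal look harder to meet than it is. It does not affect N, power, alpha, the operative decision rule or the trial's verdict. It should be corrected because it misstates a pass/fail threshold for a primary endpoint and the correction is nearly free.

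**What to change.** The simplest change is to delete the third column from the efficacy table in the protocol synopsis, Protocol 14.1.1 and SAP 6.1, since the real threshold depends on the observed SD. If the column is kept, replace its values with 11.35, 11.41, 11.45, 11.49, 11.55 and 11.59 for N = 86, 89, 91, 93, 96 and 98. These are the computed boundaries rounded down, so that each listed mean passes. Add a label saying that they apply only if the observed SD is 17 and that success is decided by the upper 97.5% t-limit.

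The cost is one column edited twice in the protocol and once in the SAP. The analysis, sample size and decision rule do not change.
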